**Table 4: Multiple Myeloma Disease-specific Assessments**

Procedure	Notes
SPEP with M-spike quantification, and serum protein immunofixation	Per IMWG.
UPEP (24-hour urine for total protein) with M-spike quantification and urine protein immunofixation	
Per IMWG. If the patient fails to provide the 24-hour urine sample, this should be documented. All attempts should be made to collect the 24-hour urine sample at the required time points.
 
UPEP must be determined from a urine sample collected for 24 hours – no other method is acceptable.
 
UPEP must be performed at each time point outlined in the protocol even if the patient is being followed by SPEP.

Serum FLC	Per IMWG.
Quantitative Ig levels	
Per IMWG.
 
For IgA and IgD myelomas, quantitative immunoglobulin measurements are preferred for disease assessments; the same percentage changes apply as for serum M-spike. Only nephelometry can be used for the response assessment, and SPEP and nephelometric values cannot be used interchangeably (Durie et al., 2006).

$\beta_2$ -microglobulin	For MM staging ( Appendix 2 ), not for assessing response
Skeletal survey	
A skeletal survey (using x-rays and/or other clinically appropriate imaging modalities [MRI, whole body CT, or PET/CT]), as determined by the Investigator, will be performed within 45 days of C1 D1 and as clinically indicated, per Investigator discretion, during the study. The skeletal survey should include a lateral radiograph of skull, anteroposterior and lateral views of the spine, and anteroposterior views of the pelvis, ribs, femora, and humeri. Results will be read by the local laboratory.
 
If lytic bone lesions or plasmacytomas are observed at Screening, their number and size should be recorded in the CRF. Bone lesions and/or plasmacytomas seen at baseline should be re-assessed during the study at a frequency determined by the Investigator, using the same imaging modality that was used at Screening.
 
 
• For patients without soft tissue plasmacytomas (i.e., bone lesions only), skeletal survey by X-rays or low-dose CT should be performed. Contrast is not required.
 
• For patients with soft tissue plasmacytomas, skeletal survey by X-rays or low-dose CT should be performed (contrast not required) and in addition MRI or CT or PET/CT, usually requiring contrast enhancement, should be performed.
 

Clinical plasmacytoma	If plasmacytomas are detected at Screening by physical examination/palpation, they should be counted and measured per IMWG guidelines and recorded, and then reassessed and recorded during symptom directed physical examinations.
CCI	

Procedure	Notes
	
CCI [REDACTED]

CCI [REDACTED]
	
[REDACTED]

FACT-MM
	
See Section 9.9.2

### 9.3. Multiple Myeloma Response Criteria

IMWG criteria ([Kumar 2016](#)) will be used in this study to assess response. All MM assessments are required at each time point as outlined in this protocol ([Table 1](#)).

Response will be assessed per IMWG response criteria for multiple myeloma ([Appendix 3](#)). Two consecutive samples are required to confirm the response. The time period between samples may be discussed with the Medical Monitor and can occur on the same day, as long as, the samples are analyzed separately.

- Complete response (CR)
- Stringent complete response (sCR)
- Very good partial response (VGPR)
- Partial response (PR)
- Minimal response (MR)
- Stable disease (SD)
- Progressive disease (PD)

## 9.4. Safety Assessments

Safety evaluations will be conducted at each visit and will include the procedures summarized below.

### 9.4.1. 12-Lead ECG

A standard 12-lead ECG will be performed as indicated in [Table 1](#). Patients must rest for at least 5 minutes prior to the ECG recording. The Investigator will interpret the ECG using one of the following categories: normal, abnormal but not clinically significant, or abnormal and clinically significant. The date and time the ECG was performed and the following parameters will be recorded in the eCRF: heart rate, PR interval, QT interval, QRS interval, and QT corrected (QTc) using Bazett's formula or calculated by the Fridericia correction formula (*Bazett 1920, Fridericia 1920*). If Bazett correction is entered by the site, the Fridericia corrected QTc interval (QTcF) will be derived using the formula:  $QT/(RR^{1/3})$ , where  $RR = 60/\text{heart rate}$ .

### 9.4.2. Ophthalmic Exam

A full ophthalmic examination will be performed prior to the patient's first dose of selinexor. Prior to dilation, best corrected visual acuity (Snellen's Equivalent based on either Snellen chart or ETDRS chart), slit lamp examination including tonometry, following dilation, and funduscopy. If a cataract is seen during the examination, the cataract will be graded as follows:

- *Lens Opacities Classification System III (LOCS III)* – Patients who enrolled in this study under the original Protocol or Protocol Amendments 1 or 2 and had detectable cataracts graded according to the LOCS III will continue to have their cataracts graded according to LOCS III and will not switch to the new AOA Grade 1-4 cataract scale. For new patients or patients in whom no cataracts have been detected to date, if cataracts are detected, they will be graded according to the Grade 1-4 scale.
- *American Optometric Association (AOA) Cataract Grading System* – Starting with Protocol Amendment 3, new patients will be evaluated using the AOA grading system until they complete the study. This system is modified from the Optometric Clinical Practice Guideline: Care of the Adult Patient with Cataract, which is available on the AOA website ([www.aoa.org](http://www.aoa.org))(See [Appendix 5](#).)

### 9.4.3. Clinical Laboratory Assessments

The following clinical laboratory tests should be performed as indicated in [Table 1](#).

- Hematology (blood sample: ethylenediaminetetraacetic acid [EDTA]) tests including hemoglobin, hematocrit, mean corpuscular volume, mean corpuscular hemoglobin, mean corpuscular hemoglobin concentration, white blood cell (WBC) count, WBC differential, red blood cell count, lymphocytes, monocytes, neutrophils, eosinophils, basophils, and platelets. WBC differential may be automated or manual as per institutional standards.

- Serum Chemistry (blood sample: serum)
  - Complete Serum Chemistry will include sodium, potassium, chloride, bicarbonate ( $\text{HCO}_3^-$ ), blood urea nitrogen (BUN), creatinine, glucose, calcium, phosphate, magnesium, ALT, AST, alkaline phosphatase, LDH, total protein, albumin, amylase, lipase, creatine kinase and uric acid.
  - Limited Serum Chemistry will include sodium, potassium, chloride, bicarbonate, BUN, creatinine, glucose, ALT, AST, alkaline phosphatase, total bilirubin and LDH, unless otherwise clinically indicated.
  - Thyroid-stimulating hormone (TSH)
- Coagulation parameters will include prothrombin time (PT), international normalization ratio (INR), and activated partial thromboplastin time (aPTT).
- Urinalysis will include appearance, color, urine bilirubin, glucose, hemoglobin, ketones, pH, protein, specific gravity, and urobilinogen. Microscopy will only be performed if clinically indicated.

Blood chemistry will be analyzed at each study site by a certified local laboratory and a report of the laboratory values will be provided to the Investigator. The Investigator or designee will review the laboratory results and assess the clinical significance of all abnormal values. Appropriate action will be taken for any clinically significant abnormal values. Values will be documented on the laboratory report until stabilized, or the laboratory value returns to a clinically acceptable range (regardless of relationship to study medication) or baseline. Any laboratory value that remains abnormal at the EoT Visit and that is considered clinically significant will be followed according to accepted medical standards for up to 30 days or until resolution of the abnormality or return to baseline. Toxicity will be assessed using CTCAE version 4.03.

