5.3. LABORATORY SAFETY VARIABLES

5.3.1. Definitions

Clinical laboratory data consists of blood analysis, including hematology, serum chemistry, coagulation parameters, and urinalysis. Clinical laboratory values in conventional units will be converted using the international system of units (SI).

Blood samples for clinical laboratory tests will be taken as specified in the study protocol. The laboratory parameters will be classified as follows:

- Hematology (blood sample: ethylenediaminetetraacetic acid [EDTA]) tests including hemoglobin, hematocrit, mean corpuscular volume, mean corpuscular hemoglobin, mean corpuscular hemoglobin concentration, white blood cell (WBC) count, WBC differential, red blood cell count, lymphocytes, monocytes, neutrophils, eosinophils, basophils, and platelets. WBC differential may be automated or manual as per institutional standards.
- Serum Chemistry (blood sample: serum)
 - Complete Serum Chemistry will include sodium, potassium, chloride, bicarbonate (HCO_3^-), blood urea nitrogen (BUN), creatinine, glucose, calcium, phosphate, magnesium, alanine aminotransferase (ALT), aspartate aminotransferase (AST), alkaline phosphatase, total bilirubin and lactate dehydrogenase (LDH), total protein, albumin, amylase, lipase, creatine kinase and uric acid.
 - Limited Serum Chemistry will include sodium, potassium, chloride, bicarbonate, BUN, creatinine, glucose, ALT, AST, alkaline phosphatase, total bilirubin and LDH, unless otherwise clinically indicated.
- Thyroid-stimulating hormone (TSH)

- Coagulation parameters will include prothrombin time, international normalization ratio (INR), and activated partial thromboplastin time (aPTT).
- Urinalysis will include appearance, color, urine bilirubin, glucose, hemoglobin, ketones, pH, protein, specific gravity, and urobilinogen. Microscopy will only be performed if clinically indicated.

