5.3.2. Analysis of Laboratory Variables

Whenever applicable, severity of selected clinical laboratory measures will be determined based on the CTCAE criteria. The worst toxicity grade in hematology and chemistry will be summarized by toxicity grade. Shift tables that present changes from baseline to worst on-study and baseline to last on-study values relative to CTCAE classification ranges will be presented.

For several key laboratory parameters (e.g., sodium, creatinine, platelet, hemoglobin, WBC, BUN-to-creatinine ratio, urea-to-creatinine ratio), box plots on measurements over time may be presented.

A listing of possible Hy's law cases (ALT or AST > 3 x upper limit of normal [ULN] with simultaneous total bilirubin > 2 x ULN) will be presented. The elevations of ALT/AST and total bilirubin must occur within 2 days of each other.

Thresholds/Range analyses for selected laboratory, vital signs, and ECG parameters will be conducted. Please refer to Appendix 7.2 for the definitions on thresholds/ranges for selected parameters. The number and percentage of patients classified into each category based on worst values will be presented.

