Total Cholesterol	>ULN - \leq 7.75 mmol/L >7.75 - \leq 10.34 mmol/L >10.34 - \leq 12.92 mmol/L >12.92 mmol/L	CTCAE grade 1-4
Triglycerides	>1.71 - \leq 3.42 mmol/L >3.42 - \leq 5.7 mmol/L >5.7 - \leq 11.4 mmol/L >11.4 mmol/L	CTCAE grade 1-4
Glucose	Hypoglycemia <LLN - \geq 3.0 mmol/L <3.0 - \geq 2.2 mmol/L <2.2 - \geq 1.7 mmol/L <1.7 mmol/L	CTCAE grade 1-4
	Hyperglycemia >ULN - \leq 8.9 mmol/L >8.9 - \leq 13.9 mmol/L >13.9 - \leq 27.8 mmol/L >27.8 mmol/L	CTCAE grade 1-4
Albumin	<LLN - \geq 30 g/L <30 - \geq 20 g/L <20 g/L	CTCAE grade 1-3

Amylase	>ULN - $\leq 1.5 \times$ ULN >1.5 - $\leq 2.0 \times$ ULN >2.0 - $\leq 5.0 \times$ ULN >5.0 x ULN	CTCAE grade 1-4
Lipase	>ULN - $\leq 1.5 \times$ ULN >1.5 - $\leq 2.0 \times$ ULN >2.0 - $\leq 5.0 \times$ ULN >5.0 x ULN	CTCAE grade 1-4
Direct bilirubin	>ULN - $\leq 1.5 \times$ ULN >1.5 - $\leq 2 \times$ ULN >2 - $\leq 3 \times$ ULN >3 - $\leq 10 \times$ ULN >10 x ULN	Same Criteria as Total Bilirubin No CTCAE Not in DILI Guidance
GGT	>ULN - $\leq 2.5 \times$ ULN >2.5 - $\leq 5.0 \times$ ULN >5.0 - $\leq 20.0 \times$ ULN >20.0 x ULN	CTCAE grade 1-4
Total protein	<LLN >ULN	No CTCAE
LDH	<LLN >ULN	No CTCAE
Calcium	Hypercalcemia >ULN - ≤ 2.9 mmol/L >2.9 - ≤ 3.1 mmol/L >3.1 - ≤ 3.4 mmol/L >3.4 mmol/L	CTCAE grade 1-4
	Hypocalcemia <LLN - ≥ 2.0 mmol/L <2.0 - ≥ 1.75 mmol/L <1.75 - ≥ 1.5 mmol/L <1.5 mmol/L	CTCAE grade 1-4
Magnesium	Hypermagnesemia >ULN - ≤ 1.23 mmol/L	CTCAE grade 1, 3, 4

	
>1.23 – ≤ 3.30 mmol/L >3.30 mmol/L
	No CTCAE grade 2
	
Hypomagnesemia <LLN - ≥ 0.5 mmol/L <0.5 – ≥ 0.4 mmol/L <0.4 – ≥ 0.3 mmol/L <0.3 mmol/L
	CTCAE grade 1-4
Bicarbonate	
<LLN >ULN
	No CTCAE
Inorganic phosphate	
Hypophosphatemia <LLN - ≥ 0.8 mmol/L <0.8 – ≥ 0.6mmol/L <0.6 – ≥ 0.3 mmol/L <0.3 mmol/L
	CTCAE grade 1-4
Vitamins: A, D (25-hydroxy), E, K, B12	<LLN	No CTCAE
LDL	>ULN	No CTCAE
HDL	<LLN	No CTCAE
ALT	
>ULN - ≤ 3 xULN >3 – ≤ 5 xULN >5 – ≤ 8 xULN >8 – ≤ 20.0 xULN >20.0 x ULN
	Per FDA DILI Guidance Jul 2009 and CTCAE
AST	
>ULN - ≤ 3 xULN >3 – ≤ 5 xULN >5 – ≤ 8 xULN >8 – ≤ 20.0 xULN >20.0 x ULN
	FDA DILI Guidance and CTCAE
ALT or AST	ALT>3xULN or AST>3xULN	FDA DILI Guidance

Alkaline Phosphatase	>ULN - \leq 1.5xULN >1.5 - \leq 2.5 xULN >2.5 - \leq 5.0 x ULN >5.0 - \leq 20.0 x ULN >20.0 x ULN	FDA DILI Guidance and CTCAE
Total Bilirubin	>ULN - \leq 1.5 x ULN >1.5 - \leq 2 x ULN >2 - \leq 3 x ULN >3 - \leq 10 x ULN >10 x ULN	FDA DILI Guidance and CTCAE

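### The protocol's complete chemistry panel omits total bilirubin, although the SAP lists it there and needs it for the Hy's law listing

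*Protocol*

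**What the plan says.** Protocol 9.4.3 defines two serum chemistry panels.

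- **Complete panel.** It starts with electrolytes, renal markers, glucose, calcium and phosphate and finishes with "magnesium, ALT, AST, alkaline phosphatase, LDH, total protein, albumin, amylase, lipase, creatine kinase and uric acid". Total bilirubin is not in it.
- **Limited panel.** It finishes with "ALT, AST, alkaline phosphatase, total bilirubin and LDH, unless otherwise clinically indicated".

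SAP 5.3.1 repeats both panels, but its complete panel reads "alkaline phosphatase, total bilirubin and lactate dehydrogenase (LDH), total protein, albumin, amylase, lipase, creatine kinase and uric acid". The same section says "Blood samples for clinical laboratory tests will be taken as specified in the study protocol".

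Protocol Table 1, reproduced as SAP Table 7-1, sets the timing. Complete chemistry is at Screening (or pre-dose on C1D1 under footnote 5), C2D1, Day 1 of Cycle 3 and later, and EoT. Limited chemistry is at C1D8, C1D15 and C2D15 only.

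SAP 5.3.2 plans a listing of possible Hy's law cases: ALT or AST above 3 × ULN with total bilirubin above 2 × ULN. It adds that "The elevations of ALT/AST and total bilirubin must occur within 2 days of each other". SAP Table 7-2 also has threshold rows for total bilirubin alone and for ALT and/or AST combined with total bilirubin.

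**The concern.** The SAP plans hepatic safety outputs that need total bilirubin and relies on the protocol to collect it. At most visits after Cycle 1, the panel that the protocol prescribes does not contain it. A limited panel would not normally hold a liver analyte that the complete panel lacks.

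The eligibility criteria point the same way. Complete chemistry is the only chemistry panel scheduled at Screening, yet inclusion criterion 8 (Protocol 8.4) needs a total bilirubin in that window. The omission looks unintended, though the documents do not say so.

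What is at stake is how the Hy's law listing can be read. If a site follows the protocol list literally, an ALT or AST elevation on Day 1 of Cycle 3 or later can enter the listing only if a bilirubin happened to be measured outside the panel. An empty listing could then mean either that there were no cases or that there was no paired test. No planned summary in the unredacted text separates the two.

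**Working it through.** **Inputs.** Panel contents are from Protocol 9.4.3. Visits and windows are from Protocol Table 1: C1D8 and C1D15 ± 1 day; C2D1, C2D15 and later Day 1 visits ± 2 days. The 2-day pairing rule is from SAP 5.3.2. The plan gives no figure of its own to reproduce.

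**Step 1: panels side by side**

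| Panel | Protocol 9.4.3 | SAP 5.3.1 |
|---|---|---|
| Complete | no total bilirubin | total bilirubin |
| Limited | total bilirubin | total bilirubin |

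Urine bilirubin, in the urinalysis list, is a different test and does not fill the gap.

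**Step 2: post-dose visits with ALT/AST.** Take a patient who starts n ≥ 2 cycles and attends every scheduled visit.

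- With panel bilirubin: C1D8, C1D15, C2D15 = 3.
- Without: C2D1 (1) + Day 1 of Cycles 3 to n (n − 2) + EoT (1) = n.
- Share without = n/(n + 3). Leaving EoT out, because an early EoT could by chance fall near a limited-panel visit, the share is (n − 1)/(n + 2).

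| Cycles started | With EoT | Without EoT |
|---|---|---|
| 2 | 2/5 = 40% | 1/4 = 25% |
| 3 | 3/6 = 50% | 2/5 = 40% |
| 4 | 4/7 = 57% | 3/6 = 50% |
| 6 | 6/9 = 67% | 5/8 = 63% |
| 12 | 12/15 = 80% | 11/14 = 79% |

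The formula does not cover a patient who starts one cycle. There the visits are C1D8, C1D15 and EoT, so the share is 1/3 with EoT and 0/2 without.

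If the complete panel contained total bilirubin, as in SAP 5.3.1, all n + 3 visits would be covered.

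**Step 3: distance to the nearest scheduled bilirubin.** Nominal days, no dosing delay; the minimum takes both windows at their extremes.

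| Visit pair | Nominal gap | Minimum gap |
|---|---|---|
| C1D15 (Day 15) to C2D1 (Day 29) | 14 days | 14 − 1 − 2 = 11 |
| C2D1 (Day 29) to C2D15 (Day 43) | 14 days | 14 − 2 − 2 = 10 |
| C2D15 (Day 43) to C3D1 (Day 57) | 14 days | 14 − 2 − 2 = 10 |
| C2D15 (Day 43) to C4D1 (Day 85) | 42 days | 42 − 2 − 2 = 38 |

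Every gap exceeds 2 days, and the gap keeps growing after C4D1. Under the written schedule, a limited-panel bilirubin therefore cannot be paired with ALT/AST from C2D1 or from Day 1 of any later cycle.

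**Step 4: does a version difference explain it?** SAP 1.7 says the SAP is based on Protocol v5.0, and the protocol supplied is v6.0. The v6.0 summary of changes names no change to 9.4.3, and the visible part of SAP 1.7 names no change to the laboratory panels. Nothing visible attributes the mismatch to versions, although the v5.0 panel itself cannot be seen.

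**The case against.** The strongest reply is that the mismatch is textual and may have little effect on the data.

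- **Bilirubin may be measured anyway.** The protocol says "Blood chemistry will be analyzed at each study site by a certified local laboratory", and a local laboratory may report bilirubin unasked. The panel wording does not forbid extra analytes. Investigators must review the results and act on clinically significant abnormalities. This stands, and it is why the point concerns the schedule rather than missing data.
- **Possible cases are bounded.** Table 7-2 has a stand-alone row for "ALT>3xULN or AST>3xULN", and Protocol 13.3 promises by-patient listings, so a reader can check by hand. This stands in part. SAP 5.3.2 says "The number and percentage of patients classified into each category based on worst values will be presented", so the row counts patients and does not show which elevations had a paired bilirubin.
- **The combined rows in Table 7-2 do not state the 2-day rule.** They might combine an early bilirubin with a later ALT or AST. They still need a measured bilirubin, and none is scheduled after C2D15.
- **Intent is not proven.** The v4.0 change log for 9.4.3 mentions removing parameters that were not needed. It does not name bilirubin. A site can also meet criterion 8 with a test outside the panel, so that criterion is evidence of a slip, not a strict contradiction. Whatever the intent, the protocol and SAP panels still differ.
- **The percentages count visits, not missed cases.** Correct. The documents give no distribution of treatment duration, and the high figures apply only to patients who stay on treatment for many cycles.
- **The safety analyses are descriptive.** Also correct, and it limits the weight of the point.

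**Conclusion.** The point holds. Protocol 9.4.3 and SAP 5.3.1 contradict each other on the complete panel, and the SAP defers to the document that leaves the analyte out. As written, C2D1, Day 1 of Cycle 3 and later, and EoT carry ALT/AST without a panel bilirubin. That is 40% of post-dose ALT/AST visits for a patient starting 2 cycles and 80% for one starting 12 (25% and 79% without EoT).

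These shares assume literal adherence to the panel, full attendance and at least 2 cycles started. The gaps assume no dosing delay. No single share applies to the trial: SAP 1.4 sets no maximum treatment duration, and the primary analysis takes place once all patients have completed the Cycle 2 myeloma assessments, so follow-up will vary.

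The effect is confined to on-treatment hepatic safety outputs. Baseline bilirubin is secured by criterion 8, and the ORR analysis is untouched. It should be corrected, but it does not threaten the trial's main conclusion.

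**What to change.** Reconcile the two sections by adding total bilirubin to the complete panel in Protocol 9.4.3, so that it matches SAP 5.3.1 and supports the outputs in SAP 5.3.2 and Table 7-2.

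For visits already completed, the SAP could add one optional count: of all ALT or AST results above 3 × ULN, how many had a total bilirubin within 2 days. That would let a reader tell an absence of cases from an absence of paired tests.

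The cost is one analyte name in one line and one routine test on a sample already drawn. Protocol 14.5 requires a written amendment with ethics approval and, where required, health authority approval; the change could be bundled with another amendment. The optional count uses existing data only. Any bilirubin not measured at a past visit cannot be recovered.

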#### **9.4.4. Pregnancy Testing**

For females of childbearing potential, a negative serum human chorionic gonadotropin (hCG) pregnancy test must be obtained within 3 days before the first dose of study treatment. Test sensitivity for hCG must be  $\geq 25$  mIU/mL. Pregnancy testing (serum hCG or urine) is also required for females of childbearing potential prior to dosing on Day 1 of Cycles  $\geq 2$  during the study and at the EoT Visit (serum hCG).

Pregnancy testing may also be performed as clinically indicated during the study.

### **9.5. Pharmacokinetic CCI Procedures**

#### **9.5.1. Blood Sampling and Processing**

As of protocol version 5.0, these samples are no longer collected.

#### **9.6. Pharmacokinetic Endpoints**

Pharmacokinetic analysis of selinexor plasma levels will be performed on blood samples from patients enrolled in Part 1 only. Pharmacokinetic endpoints to be evaluated include selinexor maximum plasma concentration and time-to-peak plasma concentration.

Plasma samples will be analyzed via a validated high performance liquid chromatography/tandem mass spectrometry (HPLC/MS-MS) method for plasma selinexor. Selinexor concentration data will be analyzed in a non-linear mixed effects population PK model with potential covariates including, but not limited to: age, body weight, gender, disease state, baseline hepatic or renal function, and concomitant medications. CCI

Details of the population PK analysis, including software, post-processing and statistical analysis, will be outlined in a separate Data Analysis Plan, to be completed prior to database lock.

CCI [Redacted]

CCI [Redacted]

CCI [Redacted]

CCI [Redacted]

[Redacted]

CCI [REDACTED]

CCI [REDACTED]

CCI [REDACTED]

## 9.8. Efficacy Procedures

### 9.8.1. Objective Disease Assessment

Procedures for confirming response are listed in [Table 4](#).

## 9.9. Efficacy Endpoints

The primary efficacy objective/endpoints are provided in [Section 6.1](#); secondary efficacy endpoints are presented in [Section 6.2](#).

